3.5. Coding Dictionaries

Medical history and adverse events (AEs) will be coded using Medical Dictionary for Regulatory Activities (MedDRA), Version 24.0 or higher.

Prior and concomitant medications and procedures will be coded using the World Health Organization (WHO) Drug Dictionary (MAR 2021 or higher).

Clinical laboratory parameters will be graded for toxicity as defined by the National Cancer Institute Common Terminology Criteria for Adverse Events (NCI-CTCAE), Version 5.0.

3.6. General Analysis Conventions

Continuous data will be summarized using descriptive statistics (number of patients with assessment, mean, median, standard deviation, minimum, and maximum). Categorical data will be summarized using frequencies and proportions. Time-to-event data will be reported in months, and summarized via Kaplan-Meier (KM) methodology using the 25th, 50th (median), and 75th percentiles with associated 2-sided 95% confidence intervals (CIs), and time point survival probabilities with associated 2-sided 95% CIs.

4. ANALYSIS POPULATIONS

4.1. Intent to Treat Population

The KIT Exon 11 ITT (Ex11 ITT) Population is defined as all randomized patients who are designated as having a mutation in KIT Exon 11 per IRT. Patients in this population will be analyzed according to the treatment which they were scheduled to receive.

CONFIDENTIAL Page 11 of 29

The all patients (AP) ITT Population is defined as all patients who are randomized. Patients in this population will be analyzed according to the treatment which they were scheduled to receive.

4.2. Safety Population

The Safety Population is defined as all patients who are randomized and receive at least one dose of study drug.

The KIT Exon 11 Safety (Ex11 Safety) Population is defined as all patients in the Safety population who are designated as having a mutation in KIT Exon 11 per IRT.

Safety Population and Ex11 Safety Population will be used for safety analyses and treatment assignment will be based on the actual study treatment initially received.

4.3. PK Population

The PK Population will include all randomized patients who received at least 1 dose of ripretinib and had at least 1 non-missing PK concentration in plasma reported for ripretinib or DP-5439.

4.4. Per Protocol Population

The KIT Exon 11 Per Protocol (Ex11 PP) Population is defined as all patients in the Ex11 ITT population who did not have any important protocol deviations which may affect efficacy analysis.

The All Patients Per Protocol (AP PP) population is defined as all patients in AP ITT population who did not have any important protocol deviations which may affect efficacy analysis.

The efficacy analysis based on the Ex11 PP and AP PP population will be supportive and treatment groups will be based on actual treatment received. Important protocol deviations and whether they affect efficacy will be identified and pre-specified in a separate document prior to final analysis of PFS based on IRR.

5. PATIENT DISPOSITION

Patient disposition will be summarized overall and by treatment arm. The number and proportion of patients will be displayed for each population (i.e., Ex11 ITT, AP ITT, Safety, Ex11 Safety, PK, Ex11 PP, and AP PP). The number and proportion of patients in the Safety Population and Ex11 Safety Population who have discontinued from treatment will be summarized by the primary reason for treatment discontinuation. The number and proportion of patients in the Ex11 ITT population and AP ITT population who have discontinued from the study will be summarized by the reason for study discontinuation as well.

6. PROTOCOL DEVIATIONS

A protocol deviation is any change, divergence, or departure from the study design or procedures defined in the clinical protocol. Protocol deviations will be classified by medical review prior to database snapshot for the primary analysis and important protocol deviations will be identified.

CONFIDENTIAL Page 12 of 29

An important protocol deviation is a deviation that may significantly impact the completeness, accuracy, and/or reliability of the trial data; that may significantly affect a subject's rights, safety, or well-being. All important deviations related to trial inclusion or exclusion criteria, conduct of the trial, patient management or patient assessment will be summarized and described in the CSR.

7. DEMOGRAPHIC AND BASELINE CHARACTERISTICS

7.1. Demographic Characteristics

Demographic and baseline characteristics at study entry will be summarized in the Ex11 ITT, AP ITT, Safety population, and Ex11 Safety population.

Demographic and baseline variables to be summarized are:

- Continuous variables
 - Age (years) at time of consent
 - Height (cm)
 - Weight (kg)
 - BMI (kg/m²)
- Categorical variables
 - Age Category at time of consent
 - \circ 18 64 years
 - \circ 65 74 years
 - o 75 years or older
 - Gender
 - o Female
 - o Male
 - Race
 - o Black or African American
 - American Indian or Alaska Native
 - o Asian
 - o Native Hawaiian or Other Pacific Islander
 - White
 - Not Reported
 - o Other
 - Race Category
 - White
 - o Non-white
 - Not Reported
 - Ethnicity

CONFIDENTIAL Page 13 of 29

- Not Hispanic or Latino
- Hispanic or Latino
- Not Reported
- o Unknown
- Region
 - North America
 - South America
 - o Europe
 - o Asia-Pacific
- ECOG Score at Screening
 - \circ 0
 - 0 1
 - 0 2
- Mutation Type per EDC
 - o KIT exon 9
 - o KIT exon 11
 - o KIT/PDGFRA WT
 - o other KIT {absence of exon 9 or 11}/PDGFRA
- Intolerance to Imatinib per EDC
 - o Yes
 - o No
- Mutation Type per IRT
 - o KIT exon 9
 - o KIT exon 11
 - o KIT/PDGFRA WT
 - o other KIT {absence of exon 9 or 11}/PDGFRA
- Intolerance to Imatinib per IRT
 - o Yes
 - o No

7.2. Medical History

The number and percentage of patients with each medical history condition will be summarized for the Safety Population and Ex11 Safety Population by System Organ Class (SOC) and Preferred Term (PT) as coded using MedDRA in the Ex11 ITT, AP ITT, Safety Population, and Ex11 Safety Population.

7.3. Cancer History and Prior Cancer Therapy

Time since the initial diagnosis in years (calculated from initial diagnosis to the date of randomization), stage, site of primary tumor, histology of primary tumor, and baseline tumor burden by IRR and by INV, respectively, as measured by number of target lesions and sum of

CONFIDENTIAL Page 14 of 29

longest diameters of the target lesions at baseline will be summarized for the Ex11 ITT, AP ITT, , Safety Population, and Ex11 Safety Population.

For prior imatinib therapies for GIST, the following data will be summarized overall and by treatment arm: number of patients who were treated with prior imatinib therapy, number of patients treated in a given clinical setting among any prior imatinib regimens, clinical setting of the most recent imatinib therapy (neoadjuvant, adjuvant, locally advanced, metastatic, unknown), best overall response to the most recent imatinib therapy, reason for discontinuation from the most recent imatinib therapy, time since the start of the first imatinib therapy, and time from the end date of the most recent imatinib therapy.

Prior surgery and radiation therapies for GIST will be summarized overall and by treatment arm.

Cancer history of GIST, prior imatinib therapies, prior surgeries for GIST, and prior radiation therapies for GIST will be summarized in the Ex11 ITT, AP ITT, Safety Population, and Ex11 Safety Population.

8. EFFICACY ANALYSIS

8.1. Primary Endpoint

8.1.1. Primary Analysis

The primary endpoint of PFS based on IRR is defined as the time interval between the date of randomization and the earliest documented evidence of the first disease progression based on IRR or death due to any cause, whichever occurs first.

Special rules of defining an event or censoring PFS are as follows:

- For patients who do not have adequate tumor assessment at baseline (adequate baseline is defined as having baseline assessment ≤31 days before the date of first dose or date of randomization if the patient did not receive study treatment) or do not have any adequate post-baseline assessments (defined as non-missing and evalulable assessment), PFS will be censored at randomization date (PFS=1 day) unless they die ≤14 weeks from the date of randomization, they will be considered to have a PFS event at death date.
- For patients who received a new anticancer therapy (including surgical resection on GIST lesions, radiotherapy of GIST lesions, or an anticancer treatment other than the study treatment) before event, PFS will be censored at the date of the latest evaluable progression-free tumor assessment prior to the start of new anticancer therapy. If date of progression occurs on the same date of as the start of new anti-cancer therapy, the progression will be counted as an event.
- For patients who did not have disease progression and did not die, PFS will be censored at the time of the latest date of evaluable progression-free tumor assessment.
- For patients who have first disease progression or die after two or more consecutive missed/non-evaluable assessments since the last evaluable tumor assessment, PFS will be censored at the time of the last evaluable progression-free tumor assessment.

CONFIDENTIAL Page 15 of 29

PFS (months) = [(date of event or censoring - date of randomization) +1]/30.4375

The primary endpoint PFS will be analyzed in both Ex11 ITT Population and AP ITT Population.

Analysis for PFS in Ex11 ITT population will be stratified by intolerance to imatinib per IRT [yes vs. no]. Analysis for PFS in AP ITT population will be stratified by the randomization stratification factors per IRT (mutation status [KIT exon 9 vs. KIT exon 11 vs. KIT/PDGFRA WT vs. other KIT {absence of exon 9 or 11}/PDGFRA] and intolerance to imatinib [yes vs. no]).

The p-value from a 2-sided stratified log-rank test at 0.05 significance level will be used for evaluation of treatment difference. Point estimate of hazard ratio will be obtained from a Cox proportional-hazards regression model stratified by randomization stratification factors per IRT and the associated 95% CI will be obtained using Wald method. PFS time will be summarized via Kaplan-Meier (KM) methodology using the percentiles (25th, 50th [median], and 75th), survival probabilities at pre-specified timepoints with associated 2-sided 95% confidence intervals, and KM plot of the estimated survival functions.

8.1.2. Supportive and Sensitivity Analyses

Supportive analysis of the primary endpoint PFS based on IRR in the PP populations and the sensitivity analyses of PFS will be performed in an analogous fashion as the primary analysis.

Supportive analysis of the primary endpoint PFS in the PP populations will include the following:

- PFS based on IRR using mRECIST criteria in Ex11 PP population
- PFS based on IRR using mRECIST in AP PP population

Sensitivity analyses will include the following:

- PFS based on IRR using mRECIST criteria stratified by intolerance to imatinib treatment per EDC in Ex11 ITT population based on mutation status per EDC (note: this analysis is performed only in the case that the mutations status per EDC and intolerance to Imatinib per EDC are not consistent with the randomization stratification factors per IRT)
- PFS based on IRR using mRECIST criteria stratified by mutation status per EDC and intolerance to imatinib treatment per EDC in AP ITT population (note: this analysis is performed only in the case that the mutations status per EDC and intolerance to Imatinib per EDC are not consistent with the randomization stratification factors per IRT)

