8.3.5. Time to Tumor Progression

TTP is defined as the interval between the date of randomization and the earliest documented evidence of disease progression.

Censoring rules for TTP will be same as those specified for PFS in Section 8.1.1. Additionally, patients who died without documented progression will be censored at the latest date of evaluable progression-free tumor assessment.

TTP (months) = [date of event or censoring – date of randomization +1]/30.4375 TTP will be analyzed in a similar fashion as PFS.

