8.3.6. PFS Based on Investigator Assessment

As a sensitivity analysis to the primary efficacy analysis, PFS based on Investigator assessment (INV) is defined as the interval between the date of randomization and the earliest documented evidence of disease progression based on INV or death due to any cause, whichever occurs first. Special rules for defining a PFS event or censoring PFS based on Investigator assessment will be similar to those specified for the primary endpoint PFS in Section 8.1.

PFS based on INV will be analyzed in an analogous fashion to PFS based on IRR. As noted in Section 8.1, the following analyses will be performed based on the Investigator assessment and used as sensitivity analyses for the primary endpoint PFS based on IRR:

- PFS based on INV using mRECIST criteria in Ex11 ITT population
- PFS based on INV using mRECIST criteria in AP ITT population

In addition to the sensitivity analyses based on the investigator assessment, the discordance between the IRR and INV will be summarized.

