8.3.7. Efficacy Based on Choi Criteria by Independent Radiologic Review

The analyses of the endpoints PFS, ORR, and TTP based on IRR will be repeated using the tumor assessments per Choi criteria among patients evaluable for Choi (CT scan present at least partially at baseline assessment and at at least one post-baseline assessment).

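### No planned analysis of mRECIST IRR PFS relaxes the SAP 8.1.1 censoring rules; separately, Protocol Table 9's fixed 100 mg restart fits only patients who were on 150 mg

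*SAP*

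**What the plan says.** **PFS.** SAP 8.1.1 defines PFS by IRR and then sets special rules. Three of them can remove an event that is on record:

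- New anticancer therapy, which includes surgery or radiotherapy of GIST lesions: "PFS will be censored at the date of the latest evaluable progression-free tumor assessment prior to the start of new anticancer therapy".
- Missed scans: "For patients who have first disease progression or die after two or more consecutive missed/non-evaluable assessments since the last evaluable tumor assessment" are censored at the last evaluable progression-free scan.
- No adequate baseline or post-baseline scan: "PFS will be censored at randomization date (PFS=1 day) unless they die ≤14 weeks from the date of randomization".

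Protocol 9.8.5.1 leaves the PFS sensitivity analyses to the SAP. SAP 8.1.2 lists the two per-protocol populations and a re-run using EDC instead of IRT values for mutation status and imatinib intolerance. The re-run is done only if the two sources disagree. Of all these it says "the sensitivity analyses of PFS will be performed in an analogous fashion as the primary analysis".

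Related analyses are in SAP 8.3. For TTP, "Censoring rules for TTP will be same as those specified for PFS in Section 8.1.1", and deaths without progression are censored as well. For investigator PFS, "Special rules for defining a PFS event or censoring PFS based on Investigator assessment will be similar to those specified for the primary endpoint", and "the discordance between the IRR and INV will be summarized". For Choi, "The analyses of the endpoints PFS, ORR, and TTP based on IRR will be repeated using the tumor assessments per Choi criteria", among Choi-evaluable patients.

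**Bilirubin dosing.** Protocol Table 9 has one row for Grade 2 and one for Grade 3 or 4. Both interrupt ripretinib until recovery and then restart it at 100 mg, without reference to the dose at onset. The Grade 3 or 4 row adds permanent discontinuation if Grade 3 or higher recurs. Table 5 gives the dose levels as 150, 100 and 50 mg. Section 5.4.2 discontinues a patient who needs less than 50 mg.

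**The concern.** The trial is open-label (Protocol 5.11), so the reasons for stopping, switching or missing scans may differ by arm. Some censoring can also follow response: Protocol 5.12.4 allows a patient in partial response to have residual tumour resected after 12 months on treatment, and then censors that patient. SAP 10.1 anticipates visits missed because of COVID-19, but SAP 10.2 only lists and tabulates them. PFS in Ex11 ITT is first in the testing order of SAP 8.5, so every later claim depends on it. If its hazard ratio is sensitive to these rules, nothing pre-specified would show it. An analysis chosen after the results are known would carry less weight.

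The Table 9 point is a safety point and has no connection with the first. Read literally, the table can put a patient back on the dose at which bilirubin rose, or on twice that dose.

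**Working it through.** **1. The plan's own event counts.** Inputs from SAP 2.3: two-sided 0.05, 1:1 allocation, HR 0.667 with 262 events (AP) and HR 0.556 with 151 events (Ex11).

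- Schoenfeld: D = 4(z₀.₉₇₅ + z₀.₉₀)² / (ln HR)² = 4(1.960 + 1.282)² / (ln 0.667)² = 256.3, so 257. Freedman: (1.960 + 1.282)² × (1.667/0.333)² = 263.3, so 264. The stated 262 lies between them.
- Power at 262 events: Φ(√262/2 × 0.405 − 1.960) = 0.906. Power at 151 events: Φ(√151/2 × 0.587 − 1.960) = 0.950.

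Both figures reproduce. The event targets are not in question.

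**2. What each planned analysis changes.**

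| Analysis | What changes | SAP 8.1.1 rules relaxed? |
|---|---|---|
| Per-protocol PFS by IRR (8.1.2) | population | no |
| EDC-strata PFS by IRR (8.1.2) | source of mutation and intolerance data | no |
| Investigator PFS (8.3.6) | assessor | no, similar rules |
| Choi PFS by IRR (8.3.7) | tumour criterion, evaluable subset | no, analysis repeated |
| TTP (8.3.5) | deaths also censored | no |
| OS (8.2.2) | deaths only | rules do not apply, but progressions are not counted |

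**3. Three constructed patients.** Cycle n Day 1 falls on day 42(n − 1) + 1, and PFS in months is days/30.4375. Assume randomization on Day 1.

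- *Missed scans.* Progression-free at Cycle 4 Day 1 (day 127), misses Cycles 5 and 6, IRR progression at Cycle 7 Day 1 (day 253). SAP 8.1.1: censored at 127/30.4375 = 4.2 months. Counting the event: 253/30.4375 = 8.3 months.
- *Surgery on study.* Partial response, resection after 12 months, drug resumed, later IRR progression. Protocol 5.4.1 interrupts ripretinib only for days around surgery, and Section 5.4 keeps assessments running during interruptions, so the later progression can be on record. SAP 8.1.1: censored at the last evaluable scan before surgery.
- *No adequate post-baseline scan.* Death on day 112 (week 16, past the 98-day limit). SAP 8.1.1: censored at day 1. Counting the death: 112/30.4375 = 3.7 months.

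No IRR-based PFS or TTP analysis in the table recovers these events. OS counts the death.

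**4. Who can be recovered.** Table 1 of the protocol schedules no imaging after the end-of-treatment visit. Survival follow-up is by telephone (Protocol 6.10.2). For a patient who stops study drug for another therapy, counting all documented events can therefore add little beyond deaths. For a patient who stays on drug after surgery, radiotherapy or missed visits, it can add IRR progressions. A patient with no later documented event stays censored under any rule.

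**5. Table 9.** Ratio = 100 mg / dose at onset.

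| Dose at onset | Table 9 restart | Ratio | One level down |
|---|---|---|---|
| 150 mg | 100 mg | 0.67 | 100 mg |
| 100 mg | 100 mg | 1.00 | 50 mg |
| 50 mg | 100 mg | 2.00 | below the lowest level |

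Table 9 itself creates the second row. A first Grade 2 event at 150 mg puts the patient on 100 mg. The recurrence rule covers only Grade 3 or higher, so a second Grade 2 event leads back to 100 mg.

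**The case against.** **PFS.** The plan is not without checks. Choi PFS and TTP change what counts as an event, and SAP 8.3.6 names investigator PFS as a sensitivity analysis of the primary endpoint. OS counts every death and is examined at the PFS analysis (SAP 2.3). Protocol 6.10.1 asks for a scan before stopping for clinical progression, and for IRR confirmation before stopping for radiological progression, which limits the problem at source. All of this stands. A reader might infer that no alternative event definition is planned at all, and the documents do not support that. The gap is narrower: none of these analyses relaxes the three rules for mRECIST IRR PFS.

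The proposed analysis also has limits. It will partly reflect later therapy, and for patients who leave study drug it mostly adds deaths. That is a reason to label it a partial check, not to omit it.

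**Table 9.** The Grade 3 or 4 row describes 100 mg as the reduced dose, which suggests that onset at 150 mg was assumed; for that patient the instruction is right. Section 5.4.2 lets the investigator reduce at any time. Bilirubin increase is not among the events in at least 10% of patients in Table 3. A reader might take Table 10 as showing that the protocol otherwise steps down one level at every grade. It does not: its one-level reduction applies to Grade 3 or 4 only, and for Grade 2 Table 9 is the stricter of the two. What stands is that the wording is wrong for onset at 100 or 50 mg.

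**Conclusion.** Both points hold, as separate and modest ones.

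On PFS, the absence is a matter of text and rests on no assumption. Its size is unknown: the documents do not say how many patients will have an event removed by these rules, or how they will split by arm. Two stronger readings are tempting.

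- *That the 20% dropout allowance in SAP 2.3 counts the affected patients.* It gives 0.20 × 426 = 85 patients, about half of the 426 − 262 = 164 without an event. But it is a planning allowance for stopping without IRR progression or death. The rules matter only where an event is documented later, and some deaths after stopping already count as events.
- *That the hazard ratio is known to be fragile.* Assume exponential PFS with medians of 9 and 6 months, 20% stoppers, and stoppers in one arm progressing at 0.5 to 2 times their arm's rate. Complete follow-up would then give an HR of about 0.60 to 0.75. The proposed analysis does not supply complete follow-up. Adding only stoppers' deaths, at an assumed 0.02 per month scaled by the same factor, gives about 0.67 to 0.70 against 0.68 with no shift. The wider range therefore does not measure what the fix would show, and neither range is evidence of bias in this trial.

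On Table 9, the literal instruction gives no reduction from 100 mg and a doubling from 50 mg. The case is uncommon, investigator discretion softens it, and the usual 150 to 100 mg step is unaffected.

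**What to change.** **SAP 8.1.2.** Add one supportive analysis of mRECIST PFS by IRR in Ex11 ITT and in AP ITT. It counts every documented IRR progression or death on its date, regardless of new anticancer therapy (including surgery or radiotherapy), missed assessments or the 14-week limit. Keep the same stratified log-rank test and Cox model. State that it is a partial check, because patients with no later documented event remain censored. Cost: a few lines and one table per population, with no new visits or scans and no change to the primary analysis.

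**Protocol Table 9, both rows.** Replace the fixed 100 mg with a restart one dose level below the dose at onset (150 to 100 mg, 100 to 50 mg). For onset at 50 mg, never resume above 50 mg: discontinue after Grade 3 or 4; after Grade 2, resume at 50 mg or discontinue, following discussion with the Sponsor. The Grade 2 choice is left open because stopping permanently after one resolved Grade 2 rise is debatable. Keep the rule for recurrence at Grade 3 or higher. Cost: a small wording amendment, which under Protocol 11.2 needs ethics and regulatory approval.

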8.2. Analysis of Key Secondary Efficacy Endpoints

The key secondary efficacy endpoints will be analyzed for Ex11 ITT and AP ITT populations.

8.2.1. Objective Response Rate

Best overall response (BOR) will be assessed based on reported overall tumor responses at different evaluation timepoints from the date of randomization until the first documentation of

CONFIDENTIAL Page 16 of 29

disease progression, death, surgical resection on GIST lesions or radiotherapy of GIST lesions, or start of new anticancer therapy, whichever occurs first.

BOR Based on Confirmed Responses:

- Confirmed Complete Response (CR): at least two determinations of CR at least 4 weeks apart (allowing a minus 3-day window) and before first documentation of disease progression
- Confirmed Partial Response (PR): at least two determinations of PR or better (PR followed by PR or PR followed by CR) at least 4 weeks apart (allowing a minus 3-day window) and before first documentation of disease progression (and not qualifying for a CR)
- Stable Disease (SD): at least one SD assessment (or better) ≥ 6 weeks (allowing a minus 3-day window) after the date of randomization and before first documentation of PD (and not qualifying for confirmed CR or confirmed PR).
 - Non-CR/non-PD per IRR review will be reported together as SD (applicable only to patients without target lesions at baseline per IRR): at least one non-CR/non-PD assessment (or better) ≥ 6 weeks (allowing a minus 3-day window) after the date of randomization and before first documentation of PD (and not qualifying for confirmed CR or confirmed PR).
- Progressive Disease (PD): first documentation of PD ≤ 14 weeks after the date of randomization (and not qualifying for confirmed CR, confirmed PR, or SD).
- Not evaluable (NE): all other cases.
 - Undefined per IRR review will be reported together as NE (applicable only to patients with neither target lesions nor non-target lesions at baseline per IRR)

Objective response is defined as BOR of either a confirmed CR or a confirmed PR. ORR is defined as the proportion of patients with a confirmed CR or a confirmed PR as the BOR. Patients with non-evaluable or missing response will be treated as non-responders and will be included in the denominator during calculation.

For ORR based on IRR in each treatment arm, the 95% exact binomial confidence interval will be calculated with Clopper-Pearson method. Analysis for ORR based on IRR in AP ITT will be stratified by the randomization stratification factors (mutation status [KIT exon 9 vs. KIT exon 11 vs. KIT/PDGFRA WT vs. other KIT {absence of exon 9 or 11}/PDGFRA] and intolerance to imatinib [yes vs. no]). Analysis for ORR based on IRR in Ex11 ITT will be stratified by intolerance to imatinib [yes vs. no]. For each population, the p-value from a Cochran Mantel-Haenszel (CMH) chi-square test will be used to evaluate the association between the ORR and the study treatment at 2-sided 0.05 significance level; stratified Newcombe 95% Confidence Limits (Newcombe, 1998) will be calculated for the difference in ORR based on IRR between the treatment arms. The analysis will be performed in the Ex11 ITT Population and AP ITT Population as the main analysis and in the PP population as supportive analysis.

Sensitivity analysis of ORR based on IRR will be performed in an analogous manner and include the following:

CONFIDENTIAL Page 17 of 29

- ORR based on IRR using mRECIST criteria stratified by intolerance to Imatinib treatment per EDC in Ex11 ITT population based on mutation status per EDC (note: this analysis is performed only in the case that the mutations status per EDC and intolerance to Imatinib per EDC are not consistent with the randomization strata per IRT)
- ORR based on IRR using mRECIST criteria stratified by mutation status per EDC and intolerance to Imatinib treatment per EDC in AP ITT population (note: this analysis is performed only in the case that the mutations status per EDC and intolerance to Imatinib per EDC are not consistent with the randomization strata)
- ORR based on INV using mRECIST criteria in Ex11 ITT population
- ORR based on INV using mRECIST criteria in AP ITT population

Supportive analysis of ORR in the PP populations will include the following:

- ORR based on IRR using mRECIST criteria in AP PP population
- ORR based on IRR using mRECIST criteria in Ex11 PP population
- ORR based on INV using mRECIST criteria in Ex11 PP population
- ORR based on INV using mRECIST criteria in AP PP population

